## 2.6. Sample Size

Sample size calculations were based on the hypothesized effect size of 0.40 standard deviation (SD) between intervention and control groups on fetal whole brain volume at 36–38 weeks of

gestational age, and on Bayley-III cognitive scores, BERA indicators, and eye-tracking assessment indicators at 4–6 months of age ( $\alpha=0.05$  and  $1-\beta=0.80$ ). The original protocol assumed an effect size of 0.30 SD and a 20% attrition rate, resulting in a minimum sample size of 400 participants. However, due to recruitment challenges and increased loss to follow-up during the COVID-19 pandemic, which raised the anticipated attrition rate to 33.3% and constrained available funding, a protocol amendment was made. The target sample size was revised to detect a difference of 0.40 SD between groups, generally considered moderate and likely to be of clinical importance, resulting in a lowered estimated minimum sample size from 400 to 300 participants. Effect sizes between 0.30 and 0.40 SD were chosen based on prior findings: for Bayley-III domains, Cohen's  $d$  values in developmental cohorts and preterm interventions fall within this range; neuroimaging studies show between-group brain volume differences of approximately 0.30–0.50 SD in fetuses and neonates; and intervention-related physiologic/eye-tracking changes are typically described in similar effect size terms.

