### 4.2. Baseline Characteristics

We will present characteristics of the study sample with continuous data as mean and SD or as median with 25th and 75th percentiles. Categorical variables will be presented as frequencies and percentages. We will indicate sample sizes for variables with more than 20% missing observations in the footnotes. Variables of the baseline characteristics are listed in **Table 1**, which best describe the study population, particularly in relation to child nutrition and cognition, as our predictor and outcome of interest in this analysis.

**Table 1.** Characteristics of the study sample

Variable	Definition
Baseline	
Child sex	2 categories: Female or male
Birth order	2 categories: First born or $\geq$ second-born
Municipality economic status	2 categories: High (Central and South Jakarta) or low (North and East Jakarta)
Maternal height	Maternal height in centimeters
Maternal pre-pregnancy BMI	BMI in kg/m 
Maternal hemoglobin level at baseline	Hemoglobin level in g/L
Maternal history of hypertension	2 categories: With a history of hypertension or without any history of hypertension
Maternal age	Maternal age in years
Maternal education	3 categories: No education/incomplete primary/unknown, Completed primary, Completed secondary or greater
Number of children	Number of children under 5 years old in the household
Number of household members	Total number of people in the household
Maternal marital status	3 categories: Monogamous marriage, polygamous marriage, or unmarried [single, divorced, widowed]
Maternal occupation	2 categories: Housewife or working mother
Paternal occupation	2 categories: Non-private sector and unemployed, or private sector
Monthly household expenditure	Household expenditure in Indonesian Rupiah per month
Endline	
Child age at outcome assessment	Child age in months (or gestational week for fetal brain outcome)
HOME inventory	HOME inventory score at the age of 4–6 months

Screen time	Screen time per day in minutes at the age of 4–6 months
-------------	---

HOME inventory, the Home Observation for Measurement of the Environment inventory.

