## 5. ANALYSIS OF THE PRIMARY OUTCOME(S)

### 5.1. Main Analysis

We will perform all analyses after the last participant in the follow-up study has completed their visit. We will review the characteristics of the study sample as blinded cohort. First, we will use fake IDs and scrambled group code to write the script for analysis and create dummy tables and figures. Once the script, tables, and figures are ready, we will insert the correct IDs with blinded group code (e.g., A vs. B) and create the draft of the interpretation of the results for each case (e.g., if “A” is the Control group vs. if “A” is the Intervention group). We will finally reveal the group assignments after all authors have reviewed and approved the results for the primary outcomes. Unblinded analyses will be performed for secondary analyses, such as effect modification and subgroup analyses.

For all outcomes, the primary analysis to answer each objective will be a minimally adjusted model controlling only for child age at assessment and the randomization stratification factors (maternal education and municipality economic status). In secondary analyses, we will estimate adjusted parameters by including additional covariates—baseline characteristics, as well as post-enrollment and follow-up variables—in addition to those included in the primary analyses.

Unless otherwise specified, we will use two-sided confidence intervals at the 0.05 significance level for all analyses. For example, we are not powered to conduct subgroup/effect-modification analyses, so these secondary objectives will be exploratory and considered significant at the  $\alpha=0.10$  level. All hypothesis testing in this analysis plan is based on a two-sided superiority framework.

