## 5.3. Subgroup Analyses

As a secondary objective, we will assess for potential effect modification on the primary outcomes by testing an interaction term between the allocation group and the factors listed below. We will present the differences between the Intervention and Control groups stratified by the effect modifier if the interactions are significant at  $p < 0.1$ .

- **Child sex:** Biological differences, different care practices, or other psychosocial practices may modify the effect of interventions on girls vs boys.
- **Birth order:** Compared to second-born or greater (multiparous mothers), first-born tend to be smaller and may be associated with lower development, thus modifying the effect of interventions.

- **Maternal pre-pregnancy BMI status:** Overweight/obesity may change gut microbiota, including during pregnancy; therefore, it may modify the effect of our intervention between mothers with vs without overweight/obesity using a BMI cutoff of  $\geq 25$  kg/m^2.
- **Baseline maternal anemia:** Anemia during pregnancy has been associated with slower brain development, which may modify the effect of interventions between mothers with vs without anemia.
- **Baseline maternal age:** Biological differences, differential care practices, or differential social support networks due to different maternal age may modify the effect of the interventions on child development. We will first use maternal age as a continuous variable to test interactions. Significant interactions will be further examined with stratified analyses.
- **Baseline maternal education:** Maternal education has been consistently associated with child development and may modify the effect of interventions between mothers with low vs high education. We will use a cutoff of incomplete secondary schooling (<9 years of formal education) to define “low education” and secondary completion or greater as “high education”.
- **Baseline socioeconomic status:** We will categorize subjects based on monthly household expenditure into quintiles, then dichotomize into the highest quintile vs. the lowest four quintiles.
- **HOME Inventory score at 4–6 months:** Children from households with lower nurturing and stimulation of the home environment may have greater potential to benefit from the intervention. We will first use the HOME Inventory score as a continuous variable to test interactions. Significant interactions will be further examined with stratified analyses.

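### Effect modification by socioeconomic status is tested on an unexplained top-fifth split of expenditure, which loses about half the information if the effect changes roughly linearly on a log or rank scale

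*SAP*

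**What the plan says.** SAP section 5.3 (under the primary outcomes) assesses effect modification by "testing an interaction term between the allocation group and the factors listed below". Stratified results are shown only when that interaction reaches p < 0.1.

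For socioeconomic status the rule is: "We will categorize subjects based on monthly household expenditure into quintiles", "then dichotomize into the highest quintile vs. the lowest four quintiles". No continuous test is mentioned, and this is the only one of the eight modifiers listed without a rationale.

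The underlying variable is recorded on a continuous scale. Table 1 in section 4.2 defines it as "Household expenditure in Indonesian Rupiah per month", and section 5.1.2 lists it in Rupiah as a potential covariate.

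Two other modifiers follow a different order. For maternal age: "We will first use maternal age as a continuous variable to test interactions". For the home environment: "We will first use the HOME Inventory score as a continuous variable to test interactions". Both are stratified only after a significant interaction.

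Pre-pregnancy BMI and anemia are also tested as two groups, but as recognised categories with a stated reason: overweight or obesity at a BMI of 25 or more, and anemia during pregnancy. The education cut at nine years matches the stratification factor in section 2.5.

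Section 5.1 says of this family of analyses that "we are not powered to conduct subgroup/effect-modification analyses", calls them exploratory and judges them at alpha 0.10. Section 2.2 names socioeconomic status among the modifiers in the secondary hypotheses.

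**The concern.** Collapsing a continuous modifier into two groups discards information about how the effect varies with it. A 20/80 cut discards more than a balanced one. It also treats the lower four fifths of households as one group, so a gradient inside that range cannot appear.

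The plan concedes that power for interactions is short and relaxes alpha to 0.10, yet for this modifier it does not use all the data it has collected. Because stratified results appear only after p < 0.1, lost power also decides whether any socioeconomic breakdown is reported at all. Nothing in the SAP suggests why the effect should change at the 80th percentile of expenditure rather than gradually or elsewhere.

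**Working it through.** **Inputs from the SAP.** Revised target of 300 participants, 0.40 SD main effect, two-sided alpha 0.05, power 0.80, anticipated attrition 33.3% (section 2.6); 157 randomised per arm (section 2.4); interaction threshold 0.10 (sections 5.1 and 5.3). The SAP gives no expenditure distribution and no power figure for any interaction.

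**The plan's own figure first.** Per arm: 2 × (1.960 + 0.842)² / 0.40² = 98.1, so 99, or 198 in total. Allowing for attrition: 198 / (1 − 0.333) = 297, against the stated 300. The figure reproduces. Evaluable children: 300 × 2/3 = 200. Using the 314 randomised gives 209; 200 is used below.

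**Information kept by the split.** For a treatment effect that changes linearly with the modifier, the fraction kept equals the squared correlation between the top-fifth indicator and the modifier.
- Normal modifier (for example log expenditure): (φ(0.842) / √(0.2 × 0.8))² = (0.280 / 0.4)² = 0.49.
- Rank (uniform) scale: 3 × 0.2 × 0.8 = 0.48.
- Effect linear in raw, skewed expenditure: exponential shape 0.65; lognormal shape, by simulation, 0.59, 0.61, 0.59, 0.52 and 0.43 for log-scale SDs of 0.3, 0.5, 0.7, 0.9 and 1.1.

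The loss is therefore 51–52% on the log or rank scale. Over the raw-scale shapes it runs from about 35% (1 − 0.65) to about 57% (1 − 0.43). If the effect changes only at the 80th percentile, the split loses nothing.

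**Detectable interaction** (200 children, 1:1, outcome in SD units, 80% power, two-sided alpha 0.10, multiplier 1.645 + 0.842 = 2.487):
- Continuous term, per SD of log expenditure: SE = 2 / √200 = 0.141; detectable 2.487 × 0.141 = 0.35.
- Split: 40 children in the top group (about 20 per arm) and 160 in the rest. SE = √(4/40 + 4/160) = 0.354; detectable difference between groups 2.487 × 0.354 = 0.88 SD.
- To put the split on the same scale: for a normal modifier the two group means lie 0.280/0.2 + 0.280/0.8 = 1.75 SD apart, so 0.88 / 1.75 = 0.50 per SD.
- Check: 0.35 / √0.49 = 0.50.

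**Power** (normal modifier). An interaction with 80% power as continuous has noncentrality 2.487. On the split this becomes 2.487 × 0.70 = 1.74, and Φ(1.74 − 1.645) is about 0.54. For an interaction of 0.3 SD per SD, power is 68% as continuous and 44% on the split.

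**The case against.** The strongest defence is that the cut is fixed in advance, in an analysis the plan itself labels exploratory and unpowered. A pre-specified cut does not bias any estimate or inflate the type I error, and it leaves no discretion over where to divide the sample. Even the continuous test needs an interaction of about 0.35 SD per SD, close to the whole planned main effect of 0.40 SD. All of this stands, and it keeps the point minor. It does not explain the cut, and the better test uses data already collected.

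A reader might infer that expenditure is the lone exception to a continuous-first rule. The SAP does not support that. BMI and hemoglobin are also recorded as continuous (Table 1) and enter section 5.3 as two groups, so three of five such modifiers are dichotomised. What distinguishes expenditure is that its cut is neither a recognised category nor given a reason.

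A reader might also take the loss of half as a fact about this trial. It depends on the assumed shape. The correlation argument runs both ways: if the effect truly jumped at the 80th percentile, it is the continuous term that would keep only 49% (normal modifier). The SAP claims no such jump.

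Finally, one might set the 0.88 SD against the 0.70 SD that a median split could detect and conclude that the variance is 1.56 times larger. Those are different contrasts: the group means lie 1.75 and 1.60 SD apart. Per SD of modifier the values are 0.88/1.75 = 0.50 and 0.70/1.60 = 0.44, and the ratio of information kept is 0.64/0.49, about 1.3. A median split is not the remedy in any case.

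**Conclusion.** The point holds as a cheap improvement to one exploratory test of a named secondary hypothesis. It is not an error or contradiction in the plan, and no primary conclusion depends on it. The size rests on about 200 evaluable children and on an effect roughly linear in log or ranked expenditure. On those terms about half the information is lost, and the detectable interaction rises from about 0.35 to 0.50 SD per SD of log expenditure. Under the other shapes examined the loss is about 35–57%. It vanishes only for a change located exactly at the cut, which the SAP gives no reason to expect.

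**What to change.** In SAP section 5.3, test the allocation-by-expenditure interaction with monthly household expenditure continuous on the log (or rank) scale, choosing one scale in advance, in the same order as for maternal age and HOME. Use the grouping into fifths only to display effects. If the top-fifth contrast is wanted for a substantive reason, state that reason before group assignments are revealed.

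The cost is a sentence of SAP wording and one changed model term; no new data are needed. The small downside is the assumption of linearity on the chosen scale.

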## SECONDARY OUTCOMES

### 5.1 Main Analysis

For all secondary outcomes, we will apply the same analytical approach used for the primary outcomes, including both the primary and secondary analyses. The primary analysis will use a minimally adjusted model, controlling only child age at assessment and the randomization stratification factors (maternal education and municipality economic status). In the secondary analyses, we will estimate adjusted parameters by adding additional covariates—baseline characteristics as well as post-enrollment and follow-up variables—in addition to those included in the primary analysis.

**Table 3. Secondary Estimands**

Secondary Estimand for Primary Analysis					
Population	Treatment	Outcome	Summary Measure	Potential intercurrent events	Strategy for intercurrent event
ITT	Initially randomised treatment (Intervention v. Control) and any subsequent changes to treatment over treatment period	Whole fetal brain volume in cm  at 36–38 weeks of gestational age (continuous)	Minimally adjusted mean difference (95%CI) between treatment arms in whole brain volume in cm  , adjusted for gestational age at assessment and the randomization stratification factors (maternal education and municipality economic status)	5. Treatment discontinuation without study withdrawal 6. Early study withdrawal 7. Treatment non-compliance (intermittent or partial treatment adherence not resulting in treatment discontinuation) 8. Dose adjustment	Treatment Policy for all intercurrent events - all observed values will be used, regardless of whether or not the subject had experienced the intercurrent event
		Cerebrum volume in cm  at 36–38 weeks of gestational age (continuous)	Minimally adjusted mean difference (95%CI) between treatment arms in cerebrum volume in cm  , adjusted for gestational age at assessment and the randomization stratification factors (maternal education and municipality economic status)		
		Deep grey matter volume in cm  at 36–38 weeks of gestational age (continuous)	Minimally adjusted mean difference (95%CI) between treatment arms in deep grey matter volume in cm  , adjusted for gestational age at assessment and the randomization stratification factors (maternal education and municipality economic status)		
		Cerebellum volume in cm  at 36–38 weeks of gestational age (continuous)	Minimally adjusted mean difference (95%CI) between treatment arms in cerebellum volume in cm  , adjusted for gestational age at assessment and the randomization stratification factors (maternal education and municipality economic status)		
		Brainstem volume in cm  at 36–38 weeks of gestational age (continuous)	Minimally adjusted mean difference (95%CI) between treatment arms in brainstem volume in cm  , adjusted for gestational age at assessment and the randomization stratification factors (maternal education and municipality economic status)		
		Bayley-III Receptive language score at 4–6 months: Z-score converted raw score of Bayley-III receptive language subscale (continuous)	Minimally adjusted mean difference (95%CI) between treatment arms in Bayley-III cognitive score, adjusted for child age at assessment and the randomization stratification factors (maternal education and municipality economic status)		

	Bayley-III Expressive language score : Z-score converted raw score of Bayley-III expressive language subscale (continuous)	Minimally adjusted mean difference (95%CI) between treatment arms in Bayley-III expressive language score, adjusted for child age at assessment and the randomization stratification factors (maternal education and municipality economic status)		
	Bayley-III Language composite score : Score based on conversion of combined Bayley-III receptive and expressive communication scaled scores (continuous)	Minimally adjusted mean difference (95%CI) between treatment arms in Bayley-III language composite score, adjusted for child age at assessment and the randomization stratification factors (maternal education and municipality economic status)		
	Bayley-III Fine motor score : Z-score converted raw score of Bayley-III fine motor subscale (continuous)	Minimally adjusted mean difference (95%CI) between treatment arms in Bayley-III fine motor score, adjusted for child age at assessment and the randomization stratification factors (maternal education and municipality economic status)		
	Bayley-III Gross motor score : Z-score converted raw score of Bayley-III gross motor subscale (continuous)	Minimally adjusted mean difference (95%CI) between treatment arms in Bayley-III gross motor score, adjusted for child age at assessment and the randomization stratification factors (maternal education and municipality economic status)		
	Bayley-III Motor composite score : Score based on conversion of combined Bayley-III fine and gross motor scaled scores (continuous)	Minimally adjusted mean difference (95%CI) between treatment arms in Bayley-III motor composite score, adjusted for child age at assessment and the randomization stratification factors (maternal education and municipality economic status)		
	IOWA cue facilitation at 6 months	Minimally adjusted mean difference (95%CI) between treatment arms in IOWA cue facilitation, adjusted for child age at assessment and the randomization stratification factors (maternal education and municipality economic status)		
	IOWA cue competition at 6 months	Minimally adjusted mean difference (95%CI) between treatment arms in IOWA cue competition, adjusted for child age at assessment and the randomization stratification factors (maternal education and municipality economic status)		

## 5.2 Sensitivity Analyses

We will not perform sensitivity analyses for secondary outcomes.

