#### **3.5. Definition of analysis populations**

For all outcomes, we will perform complete-case analysis, which include all subjects with outcome data regardless their compliance to the intervention.

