## 5.2. Sensitivity Analyses

In all primary analyses for the primary outcomes, inverse probability of censoring weights (IPCW) will be estimated to address potential bias from outcome attrition. The missingness model will be fit using logistic regression with a prespecified set of covariates, including allocation group, randomization stratification factors (maternal education and municipality economic status), baseline characteristics listed in **Table 1**, and other primary outcomes measured prior to the outcome visit (e.g., fetal whole brain volume when modeling the cognitive score) that are plausible predictors of both censoring and the outcome. Stabilized weights will be computed conditional on allocation group and the randomization stratification factors, and weights will be truncated at the 1st and 99th percentiles (0.5th and 99.5th in sensitivity analyses). Diagnostics will include summaries of the weight distribution, effective sample size, and covariate balance before and after weighting. Robustness to model misspecification will be assessed using augmented IPCW estimators.

We will not perform a per-protocol analysis given the high compliance with both the probiotics/placebo and omega-3 FAs interventions.

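### Secondary outcomes get no attrition-weighted sensitivity analysis, although censoring weights are planned for primary outcomes from the same assessments

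*SAP*

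**What the plan says.** Section 3.5 sets the analysis population: "For all outcomes, we will perform complete-case analysis, which include all subjects with outcome data regardless their compliance to the intervention". Section 5.1.1 confirms that the intention-to-treat comparison uses complete cases.

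For the primary outcomes, section 5.2 adds a check on loss: "In all primary analyses for the primary outcomes, inverse probability of censoring weights (IPCW) will be estimated to address potential bias from outcome attrition". The missingness model there uses allocation group, the stratification factors, the Table 1 baseline characteristics and primary outcomes measured before the visit in question. Weight diagnostics and augmented IPCW estimators are also planned.

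For the secondary outcomes, section 5.1 says "For all secondary outcomes, we will apply the same analytical approach used for the primary outcomes, including both the primary and secondary analyses", and then names the minimally adjusted model and the models with added covariates. Section 5.2 under the same heading reads, in full, "We will not perform sensitivity analyses for secondary outcomes".

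Section 3.9 plans tabulations of loss by arm, a comparison of children with and without outcome data, and balance checks in the retained sample. Section 2.6 gives the expected loss: the pandemic brought recruitment and follow-up problems, "which raised the anticipated attrition rate to 33.3% and constrained available funding, a protocol amendment was made".

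**The concern.** The SAP recognises that attrition may bias its estimates and builds a tool against it, then applies that tool to only some of the results from each visit. A mother who misses the MRI contributes neither whole brain volume nor any regional volume. A child who misses the Bayley-III session contributes neither the cognitive nor the language and motor scores. Section 3.10 claims the same treatment-policy estimand for primary and secondary objectives, and Table 3 lists early withdrawal just as Table 2 does.

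What is at stake is how secondary results can be read. If weighting moves whole brain volume or the cognitive score, a reader will want to know whether the regional, language or motor results from the same children move too. Under the present text no planned analysis answers that.

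**Working it through.** **1. Do the secondary outcomes share their assessment with a primary outcome?** Section 2.2 lists 5 regional volumes, 6 Bayley-III scores and 2 IOWA cue measures: 5 + 6 + 2 = 13.

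| Secondary outcomes | Primary outcome from the same assessment | SAP section |
|---|---|---|
| 5 regional brain volumes | Whole brain volume (one MRI, one segmentation) | 2.7.1 |
| 6 language and motor scores | Cognitive score (first Bayley-III assessment) | 2.7.2 |
| 2 IOWA cue measures | Mean latency and task error (one task) | 2.7.4 |

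All 13 have a partner. For the cue measures the match may be imperfect, because they need usable trials in particular cue conditions.

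**2. What handles loss for a secondary outcome?**

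- Section 3.9: descriptive checks only, with no effect re-estimated.
- Section 5.1.2, carried over by section 5.1 under Secondary Outcomes: models adjusted for covariates associated with the outcome at p < 0.1. These re-estimate the effect and can absorb loss that depends on those covariates. They do not use earlier primary outcomes. The IPCW model does, for example whole brain volume when modelling the cognitive score. This difference matters for the Bayley-III and IOWA outcomes; the MRI precedes all other primary assessments, so there is no earlier primary outcome to use for it.
- Weighted estimate: none.

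**3. Does the planning figure rest on the stated attrition?** Inputs from section 2.6 are 0.40 SD, alpha 0.05 and power 0.80; the test is two-sided (section 5.1).

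- Two-sample formula: 99 per arm, 198 in total.
- Inflation: 198 / (1 − 0.333) = 297, against 300 stated. This reproduces.
- Expected analysed: 300 × 0.667 ≈ 200, or 314 × 0.667 ≈ 209 (section 2.4 gives 157 per arm).
- Approximate 95% CI half-width in SD units: 1.96 × √(2/100.05) = 0.28, or 1.96 × √(2/104.7) = 0.27.

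**4. How large could the bias be?** The SAP gives no figure, so this is an illustration on assumed gaps. In one arm, the complete-case mean minus the full-arm mean equals f × g, where f is the missing share and g is the mean of those seen minus the mean of those lost. With the same f in both arms, the bias in the treatment difference is f × (g₁ − g₀).

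| Assumed g₁ − g₀ (SD) | f = 0.20 | f = 0.333 |
|---|---|---|
| 0 | 0 | 0 |
| 0.2 | 0.04 | 0.07 |
| 0.4 | 0.08 | 0.13 |
| 0.6 | 0.12 | 0.20 |

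The 20% column uses the attrition assumed before the amendment, only to show a range. With a common gap g but unequal loss, the bias is (f₁ − f₀) × g: a 10-point difference in loss (the example threshold in section 3.9) and an assumed gap of 0.5 SD give 0.10 × 0.5 = 0.05 SD.

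These are total biases. Weighting removes only the part that the variables in the missingness model explain.

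**The case against.** Limiting sensitivity analyses to primary outcomes is an explicit, prespecified and permissible choice, and nothing is left undefined. That stands, and it is why this is an optional improvement and not an error.

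A reader might infer that the SAP contradicts itself, because secondary outcomes are promised the same approach and then denied IPCW. The text does not support this. The promise sits under Main Analysis and spells out the minimally adjusted and covariate-adjusted models; IPCW sits in a separate sensitivity section. (Section 5.1.1 also mentions outlier sensitivity analyses, which the blanket exclusion touches. That is a separate drafting matter and does not bear on attrition.)

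A reader might also infer that secondary results stand wholly uncorrected and that selective loss would go unseen. Neither follows. The adjusted models share most of their baseline covariates with the missingness model and, if correctly specified, address loss that depends on them. The section 3.9 comparisons and the weight diagnostics for the primary outcomes would show selective attendance at a visit. What they cannot show is how far a given secondary estimate would move, since that depends on how the outcome relates to the variables driving loss, and this can differ between motor and cognitive scores.

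**Conclusion.** The point holds as an inexpensive improvement confined to the secondary outcomes. All 13 are analysed on complete cases, and none would have a weighted estimate to compare with the weighted primary estimate from the same assessment. Existing provisions protect against attrition bias only in part. Primary conclusions, sample size and power are untouched.

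The size of any shift is unknown. The range of 0.07 to 0.20 SD at 33.3% loss rests on assumed between-arm differences of 0.2 to 0.6 SD in the gap between those seen and those lost; with equal loss and equal gaps the bias is zero. It is tempting to read 33.3% as the share missing for each secondary outcome, but the SAP gives it as anticipated overall attrition and reports no observed or per-outcome rate. The MRI is prenatal and had its own pandemic opt-out (section 2.8), so its loss may differ from that at 4–6 months. Nor should one assume that a secondary estimate would shift as much as its primary partner.

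**What to change.** Replace the sentence in section 5.2 under Secondary Outcomes with:

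> For each secondary outcome the minimally adjusted model will be repeated as a sensitivity analysis with the censoring weights planned for the primary outcome from the same assessment (MRI: whole brain volume; Bayley-III: cognitive score; IOWA: mean latency), refitting the same weight model where outcome availability differs.

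The refitting clause covers the IOWA cue measures. No new data are needed. The weights are planned and not yet described as estimated, so the added work is a re-run of existing models once they are available, plus any refit. The cost is a little more analysis work and about one extra column per table.
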